Amount of dietary protein consumed during caloric restriction may be a key determinant in maintaining fatfree mass during weight loss. Adequate dietary protein is essential for skeletal muscle anabolism; and, epidemiological evidence in older adults point to a salutary effect of protein intake above the current RDA (0.8 g/kg/day) on body composition.^{17,18} Indeed, a recent position statement by the PRO-TAGE study group advises consumption of 1.0-1.2 g/kg/day in older adults *during weight-stable conditions* to aid in the maintenance of lean body mass and function.¹⁹ Practical achievement of this level of protein intake is often difficult for obese, older adults undergoing weight loss, yet may be critical to offset weight loss-associated lean mass loss. Preliminary data from our group show a lean mass sparing effect of high protein consumption during caloric restriction. In post-menopausal women undergoing a 5-month intentional weight loss program, consumption of a high (1.2 g/kg/day) versus low (0.6 g/kg/day) protein diet was associated with 50% attenuation (17% vs. 37%) of lean mass loss.²⁰ While promising, results have yet to be translated to functional changes in a tightly controlled trial of weight loss in obese, older adults.

The primary goal of this study is to determine whether adherence to a high protein (≥ 1.0 g/kg/d) weight loss program results in improved physical function by favorably affecting body composition compared to weight stability in obese, older adults. This will be accomplished by conducting a 24-week trial in 124 obese (BMI 30-42 kg/m²), older (65-79 years) men and women, at risk for mobility disability, randomized to either: (1) high protein intake (≥ 1.0 g/kg/d; n=62) during weight loss, or (2) weight-stable control (n=62).

Specific Aim 1: To compare the effects of high protein intake during weight loss versus weight stability on 24-week changes in physical function, primarily assessed by performance on the fast 400-meter walk test. *We hypothesize that participants randomized to a high protein weight loss intervention will experience greater improvements in 400-meter walk gait speed than participants who receive the weight-stable control condition.* **Specific Aim 2:** To compare the

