The second baseline testing session (BV2) will occur in the Wake Forest University Department of Health and Exercise Science. During this visit, participants will undergo muscle function tests (expanded Short Physical Performance Battery (SPPB) test, Timed-Up-and-Go (TUG) test, fast 20-meter and 400-meter walk tests, and stair climb test), DXA scan (whole body, hip and spine), physical activity questionnaire (Community Healthy Activities Model Program for Seniors; CHAMPS), quality of life questionnaire (SF-12), disability questionnaires (Pepper Assessment Tool for Disability; PAT-D and Mobility Assessment Tool-short form; MAT-sf), and instructions will be provided for a dietary run-in (approximately 30 minutes). For the dietary run-in, all participants will be provided with and oriented to the Medifast® OuickStart Guide, sample meal plans, 3, one-day dietary trackers, a sampling of 12 Medifast Meal Replacement Products, 3, one-day Product Evaluation Forms, and asked to follow the Medifast 4 &2 &1 PlanTM for a three -day period occurring over the following week. Participants will be contacted by the study registered dietitian (RD) upon completion of the dietary run in period to assess their willingness and self-efficacy to adhere to the dietary protocol for the duration of the study (24 weeks). Participants who indicate that they are willing and able to follow the protocol will be randomized (RAND) to one of the 2 study interventions (high protein weight loss group vs. weight stable control group), with blocking stratified by gender, and treated in 5 successive waves (n=12-13 participants/group/wave). Randomization of the entire wave (n=24-26) will occur approximately 1 week prior to the start of intervention, and at this time the first monthly Medifast product order will be placed for participants randomized to the high protein weight loss group.

All assessments conducted at the BV1 and BV2 testing sessions will be repeated at two follow-up visits (FV1 and FV2), occurring during the last two weeks of active intervention (weeks 23-24). Lastly, a brief midpoint visit (MP; week 12) will occur for all participants, where only DXA and fast 400-meter walk tests will be performed.

Visit	Location of Visit	Sticht	WFU	WFU	WFU	Sticht	WFU
Code	Week Number	-3	-2	-1	0-24	23	24
SV1	Informed consent, review inclusion/exclusion criteria (including demographics and BMI)	Х					

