- 2. Muscle function and strength measures include the tests described below. Each will be conducted before and after the interventions, with the exception of the 400-meter walk test, which will also be performed at the study midpoint (12-weeks). **Gait speed** will be assessed using the fast 20-meter and 400-meter walk tests. The 400-meter walk tests was originally developed in Health ABC²³ and used by our group in the CLIP and LIFE studies.^{12,24} Participants are asked to walk 10 laps of a 40-meter course (20 meters out and 20 meters back). A script is used to standardize instructions to all participants. It says: "You will be walking 10 complete laps around the course, about ¹/₄ mile. Please walk as quickly as you can, without running, at a pace you can

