- 8. Compliance and satisfaction: Although we will attempt to control compliance by the use of behavioral strategies, there may be inter-individual variability in compliance to the weight loss protocol. Therefore, participant weight will be collected at regular, bi-weekly intervals for both groups. Additionally, participants randomized to the high protein weight loss group also will be asked to provide information on daily dietary intake and complete a satisfaction survey at the end of intervention to express thoughts and feelings about following the Medifast 4 & 2 & 1 Plan. Lastly, 24-hour urine nitrogen will be assessed to ensure differential protein intake by sending participants home with a container and instructions at baseline and follow up. Participants will be asked to: (1) void at 8 AM and discard the specimen; (2) collect all urine including the final specimen voided at the end of the 24-hour collection period (i.e., 8 AM the next morning); (3) screw the lid on securely. The sample can be stored at room temperature or refrigerated for up to 14 days and when the sample is returned, it will be sent to Labcorp for analysis.

Statistical Analyses

Sample size: Unpublished data collected in older participants undergoing a 6-month weight loss intervention indicate that we can anticipate a clinically meaningful 400-meter walk gait speed difference of at least 0.05 m/s, with a common group standard deviation of 0.19 m/s and a correlation of 0.85 between baseline and 6-month measures. Using the method of Borm et al (2007),³⁴ we assume using an analysis of covariance (ANCOVA) analytic approach fitting the randomization effect and baseline gait speed, then 53 subjects completing the intervention per group will yield 80% power using a two-sided alternative hypothesis at the 0.05 level of significance. Assuming a conservative drop-out rate of 15%, we plan to enroll 124 participants (n=62/group).

Database management: To facilitate data transfer and preserve records that can be audited, we will use hard copy forms collection. All data will be manually entered within one week of collection into the study database. Our data entry system will protect confidentiality and data security and the use of text containing identifying information will be avoided. Data will reside on a server in a Microsoft SQL server database with daily backup.

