Data analyses: Regression diagnostics, residual plots, and exploratory analyses will be performed to find appropriate transformations for all variables to satisfy linearity, homogeneity of variances, and normality assumptions. Descriptive statistics consisting of frequency tables and percentages for categorical variables, and means, standard deviations, medians, and ranges for continuous variables will be tabulated and presented by intervention group and time point. Exact 95% confidence intervals (CIs) will be provided for the estimated proportions and approximate 95% CIs for estimated means. The primary outcome of the intervention effect on fast 400-meter walk gait speed will be analyzed using an ANCOVA model fit with the main effect of treatment arm and adjusted for baseline values of fast 400-meter walk gait speed. The primary test will be covariate-adjusted main treatment effect of the weight loss intervention compared to the control group, and we assume a Type I error rate of 0.05 for the two-sided alternative hypothesis. Secondary measures of body composition will be analyzed similarly, using baseline values of the particular body composition measure as a covariate in the outcome model. Other data including feasibility and compliance data collected in this study will be used to inform future studies of weight loss in older adults. All statistical analyses will be conducted assuming intent-to-treat so that participants will remain assigned to the initial randomization group regardless of treatment adherence, and participants who do not adhere or discontinue treatment will still be encouraged to provide outcomes data. Our group has past success in retaining participants by maintaining frequent contact with individuals who encounter barriers to participation and creatively accommodate and counsel, as necessary, to encourage the maximum degree of participation. To ensure the results are not overly influenced by missing data, a multiple imputation sensitivity analysis of the primary outcome will be performed using both baseline and post-randomization characteristics to inform the missing data imputation, assuming observations are missing at random.

Human Subjects Protection

Subject Recruitment Methods

We will recruit individuals using community-based recruitment strategies including mass and direct mailings and the local newspapers. We will also advertise in the VITAL newsletter (BG99-559) and participate in community outreach events.

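### The primary ANCOVA does not use the planned week-12 400-m walk, so drop-out that follows post-baseline walking speed differently in the two arms could modestly bias the week-24 effect in either direction

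*Combined protocol and SAP*

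**What the plan says.** Specific Aim 1 sets the target as "24-week changes in physical function, primarily assessed by performance on the fast 400-meter walk test". Under Statistical Analyses, Data analyses, the primary outcome "will be analyzed using an ANCOVA model fit with the main effect of treatment arm and adjusted for baseline values" of the same walk. No other term is named, and no missing-data method is given for this test.

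The assessment schedule adds a second post-baseline measurement: "Lastly, a brief midpoint visit (MP; week 12) will occur for all participants, where only DXA and fast 400-meter walk tests will be performed". The muscle function section under Study Measure(s) confirms that, among the function and strength tests, only the 400-m walk is repeated at the midpoint.

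Three other provisions bear on missing data:

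- Data analyses: "a multiple imputation sensitivity analysis of the primary outcome will be performed using both baseline and post-randomization characteristics", under missing at random.
- Data analyses: "participants who do not adhere or discontinue treatment will still be encouraged to provide outcomes data".
- Sample size: "Assuming a conservative drop-out rate of 15%, we plan to enroll 124 participants".

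The Compliance and satisfaction section adds that "participant weight will be collected at regular, bi-weekly intervals for both groups".

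**The concern.** An ANCOVA at one time point uses only participants with a week-24 walk. Given arm and baseline speed, it treats those who stayed as representative of those who left. If people leave because they are walking worse (or better) than their baseline predicts, and this happens to a different degree in the two arms, the completers' difference is not the randomized difference.

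The arms do differ in what might drive retention. One follows a 24-week meal-replacement diet. The other attends education sessions and can earn up to three months of product by attending, completing testing and staying weight-stable. This makes arm-specific selection possible, but the documents neither show that it will happen nor suggest its direction.

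The week-12 walk is the only earlier post-randomization measure of the primary outcome. Leaving it out of the test that carries the conclusion gives up information already being collected, which could remove some or all of such a bias.

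**Working it through.** **Inputs from the Sample size paragraph.** SD 0.19 m/s; baseline-to-6-month correlation 0.85; target difference 0.05 m/s; 62 per arm; 15% drop-out.

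**Assumed, because the documents give no figure.** Baseline-to-week-12 correlation 0.87; week-12-to-week-24 correlation given baseline 0.66 (range 0.3 to 0.9); drop-out odds ratio (OR) per 0.19 m/s of slower week-12 speed.

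**1. The plan's own figure.** Completers per arm for 80% power: 2 × (1.960 + 0.842)² × 0.19² × (1 − 0.85²) / 0.05² = 62.9, so 63, not the stated 53. That is a separate matter. The bias below does not depend on it. Expected completers are 62 × 0.85 = 52.7 per arm, and the standard error at 53 is 0.19 × √(1 − 0.85²) × √(2/53) = 0.0194 m/s.

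**2. Size of the bias by hand.** Suppose a fraction p leaves one arm with log-odds linear in week-12 speed, and the other arm loses people at random. To first order:

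bias ≈ p × ln(OR) × √(1 − 0.87²) × 0.66 × 0.19 × √(1 − 0.85²)

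The square roots are 0.493 and 0.527. At p = 0.15 and OR 2: 0.15 × 0.693 × 0.493 × 0.66 × 0.100 = 0.0034 m/s. OR 1.5 gives 0.0020 and OR 3 gives 0.0054.

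**3. Simulation.** 6,000 trials per scenario with a true effect of 0.05, and 6,000 under the null. Monte Carlo error is about 0.0005 m/s and 0.6 points of Type I error.

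| Drop-out (15%) | ANCOVA | With week 12 | ANCOVA Type I error |
|---|---|---|---|
| Random | 0.0499 | 0.0501 | 4.9% |
| Baseline speed only, OR 3, diet arm | 0.0504 | – | 5.1% |
| Week-12 speed, diet arm, OR 1.5 / 2 / 3 | 0.0519 / 0.0526 / 0.0548 | 0.0500 / 0.0493 / 0.0500 | 5.1 / 5.1 / 6.1% |
| Week-12 speed, control arm, OR 1.5 / 2 / 3 | 0.0483 / 0.0471 / 0.0445 | 0.0502 / 0.0504 / 0.0495 | 5.1 / 5.5 / 5.9% |
| OR 3 in one arm, 1.5 in the other | 0.0530 | – | 5.4% |
| Both arms, OR 2 / 3 | 0.0496 / 0.0500 | – | – |

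A large-sample run gives 0.0520 / 0.0533 / 0.0549 for the diet-arm row, in line with step 2. A normal approximation with standard error 0.0195 puts Type I error at 5.2% for a bias of 0.0027 and 5.8% for 0.005.

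**4. Sensitivity to the assumptions.**

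- Given-baseline correlation 0.3 to 0.9: bias 0.001 to 0.004 at OR 2, and 0.002 to 0.007 at OR 3.
- Less missing data, OR 2 to 3: 0.002 to 0.003 at 10% and 0.001 to 0.002 at 5%.
- Deliberately strong selection (log-odds 1 per baseline-adjusted SD of 0.19 × 0.493 = 0.094 m/s, an OR of exp(0.19/0.094) = 7.6 per full SD): about 0.009, with Type I error about 7%.
- Selection on the baseline-to-week-12 change instead of week-12 speed, with week-12 correlations of 0.85 to 0.922: 0.004 to 0.007 for OR 2 in one arm, and 0.009 to 0.013 for OR 2 in one arm against 0.5 in the other.

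**5. What week 12 can recover.**

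- All leavers have a week-12 walk and drop-out follows it: essentially all of the bias is removed.
- Half lack it: 0.0036 falls to 0.0018 (OR 2), and 0.0052 to 0.0026 (OR 3).
- All lack it: no gain.
- Drop-out follows unseen week-24 speed (OR 2 / 3): 0.0053 / 0.0079 falls only to 0.0030 / 0.0046.
- Precision under random drop-out: √{[(1 − 0.66²)/0.85 + 0.66²] / (1/0.85)} = 0.967, a standard error about 3% smaller.

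**The case against.** The strongest reply is that the plan already deals with most of this. Its imputation draws on post-randomization characteristics, and the week-12 walk is the obvious candidate. With that walk included, the imputation and a repeated-measures model rest on the same assumption and use much the same data. Baseline-adjusted ANCOVA with such a check is a standard design and matches the basis of the sample size. The plan also pursues outcomes after treatment stops, calls 15% drop-out conservative and keeps two-weekly contact in both arms. The bias in the moderate cases is under 0.3 standard errors, several of the simulated Type I error rates cannot be told from 5%, and every selection odds ratio is assumed.

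All of that is fair, and it is why the point ranks low. What remains is narrower. The imputation is only a sensitivity analysis. An analyst could omit the week-12 walk and still comply with the plan. Nothing says which result governs if the two disagree. Nor does changing the primary model cost anything when data are complete: with the same baseline terms at each visit, the repeated-measures week-24 contrast is essentially the ANCOVA estimate.

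**Conclusion.** The concern holds as a modest, conditional one. The primary test omits a planned measurement of its own outcome. If drop-out follows post-baseline walking speed differently by arm, the estimate shifts by about 0.002 to 0.005 m/s in the moderate one-arm cases, that is 4 to 10% of the 0.05 m/s target. The shift favours the diet if slower walkers leave the diet arm and counts against it if they leave the control arm. Larger shifts need stronger or opposing selection, or selection on change. Baseline-only or equal selection gives essentially none.

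The size rests on 15% drop-out and on week-12 correlations and odds ratios that the documents do not supply. Confidence is therefore medium, and the change is one the trial could make rather than one it must make.

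**What to change.** Make the primary test the week-24 contrast from a likelihood-based repeated-measures model of 400-m speed at weeks 12 and 24, covering all randomized participants. Include arm, visit, arm-by-visit, baseline speed and baseline-by-visit, with unstructured covariance. Keep the ANCOVA as a sensitivity analysis. In the planned imputation, name arm, baseline speed, week-12 speed and the two-weekly weights.

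If the ANCOVA stays primary, the minimum is to name those imputation variables and state in advance how a disagreement between the two analyses will be read. Either way, report by arm how many participants have week-12 and week-24 walks.

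The cost is analysis-plan wording and slightly more analysis work, with no new data, visits or staff. Missing at random is still assumed, and people who leave before the week-12 walk are not helped.

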In addition to receiving dietary counseling, all participants randomized to the high protein weight loss group will attend behavioral counseling group classes led by the RD. These classes will be held bi-weekly for the duration of the study (with an additional phone call at week 1) to provide participants an opportunity to review specific questions and problems. Group counseling sessions will provide support and introduce new topics in behavioral weight control including self-monitoring, portion control, mindful eating, coping with negative thoughts related to overeating, eating at regular times, and stress management. Weight will be measured bi-weekly, at each class, to provide additional feedback and to increase motivation. Official study baseline and post-intervention weights will occur at weeks 0 and 24 of intervention, respectively. Additionally, participants will complete daily food logs which will be reviewed by the RD to verify compliance to the diet. If it is evident, either through inadequate body weight loss or diet records, that participants are not compliant with the diet, additional individual counseling sessions with the RD will be held to improve compliance. Also, at week 24, participants in this group will be asked to complete a program evaluation form to solicit feedback on overall weight loss program product satisfaction and desired future usage, as well as product quality and taste feedback and recommendations.

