Weight Stable Control Group – Participants randomized to the weight stable control group will be monitored bi-weekly by study staff (with an additional phone call at week 1) to ensure weight stability over the course of the study. Participants will be weighed on a bi-weekly basis and encouraged to maintain weight within $\pm 5\%$ of baseline. To promote compliance and retention, participants will also be invited to bi-weekly group educational sessions, where non-weight loss health related topics (including: What is Successful Aging?, Preventing and Delaying Disease and Dysfunction, Managing Medications Effectively, and Talking Effectively with Your Healthcare Provider), will be discussed by study staff. Lastly, if weight stable participants are able to attend 75% (i.e. 9 of 12) educational sessions, all baseline and follow-up testing sessions, and maintain weight stability over the course of the study (defined as less than a 5% differential between weight measured at week 0 and 24), they will be eligible to receive up to 3 months of Medifast MRPs along with a 30-60 minute RD-led dietary instruction session on how to follow the Medifast 4 & 2 & 1 Plan.

Methods for Study Assessments

The nature, purpose, and risks of all procedures and protocols will be explained to each participant prior to obtaining written consent. All examiners are trained in the standardized conduct of all assessments before data collection. Participants will be instructed to wear appropriate and comfortable clothing, and standardized written instructions will be provided prior to each study visit.

Study Measure(s)

- 1. Height, body mass, BMI, & waist circumference. **Height** without shoes will be measured to the nearest 0.1 centimeter using a stadiometer and **body mass** will be measured to the nearest 0.1 kilogram using a calibrated and certified balance beam scale. Height and body mass will be used to calculate **BMI**. **Waist circumference** will be measured to the nearest 0.1 cm with a Gulick-II spring-retractable steel tape.

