- 7. Self-reported variables: Demographic characteristics including age, gender, race, education level, and socioeconomic status will be recorded and used as covariates if necessary. Physical activity will be measured using the CHAMPS Physical Activity Questionnaire for Older Adults at baseline and follow-up.³² Activities of daily living will be assessed using the Pepper Assessment Tool for Disability (PAT-D) at baseline and follow-up. This questionnaire covers 3 domains: (1) basic activities of daily living (ADLs) (moving in and out of a chair, moving in an out of a bed, gripping with hands, using toilet, dressing, getting in and out of a car, and bathing); (2) mobility (walking several blocks, lifting heavy objects, walking 1 block, lifting/carrying 10 lbs, climbing several flights of stairs, and climbing 1 flight of stairs); and (3) instrumental ADLs (light housework, participating in community activities, managing money, visiting with relatives or friends, using the telephone, and taking care of a family member). For each item, respondents answer whether they experience 1) no difficulty, 2) a little difficulty, 3) some difficulty, 4) a lot of difficulty, 5) unable to do or, 6) did not do for other reasons. Answers are averaged across the items, in order to better assess the overall perceived disability burden by a person. Additionally, activities of daily living will be assessed using the Mobility Assessment Tool - Short Form (MAT-sf) at baseline and follow-up. This is a novel, computerized tool for self-assessment of functional performance designed to reduce bias from factors such as age, gender and body image. The Short Form 12 (SF-12) will be used as a generic measure of health related quality of life.³³ The questionnaire consists of two norm-based composite T-scales, assessing mental health and physical function. Lastly, mood will be assessed using the 10-item Center for Epidemiologic Studies Depression Scale (CES-D).

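### The gait-speed and body-composition ANCOVAs leave out sex, the factor that stratifies the randomisation; this causes no bias, but a little power is lost if sex predicts the week-24 value beyond baseline

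*Combined protocol and SAP*

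**What the plan says.** Under Participant screening, assessments and randomization, participants are allocated "with blocking stratified by gender, and treated in 5 successive waves (n=12-13 participants/group/wave". Gender is the only stratum named.

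Under Statistical Analyses, Data analyses, the primary outcome is tested in an "ANCOVA model fit with the main effect of treatment arm and adjusted for baseline values of fast 400-meter walk gait speed". For the DXA outcomes: "Secondary measures of body composition will be analyzed similarly, using baseline values of the particular body composition measure as a covariate". The Sample size paragraph assumes the same two-term model, an "analytic approach fitting the randomization effect and baseline gait speed". The two paragraphs therefore agree, and the primary model is clearly stated.

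Sex appears as a possible covariate in one other place. In Study Measure(s), item 7, demographic characteristics including gender "will be recorded and used as covariates if necessary". No criterion is given, and no model is named.

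**The concern.** Stratified blocking makes the arms more alike on sex than simple randomisation would. If sex also predicts the week-24 value after allowing for baseline, the treatment estimate varies less from trial to trial than a model without sex assumes. That model leaves the sex variance in its error term, so it reports a standard error somewhat larger than the design achieves. The confidence interval is then wider than it need be, and a real effect is slightly more likely to be missed.

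The remark in item 7 adds a smaller difficulty. It neither puts sex in the model nor rules it out, so a choice about adjustment could be made after the data are seen.

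**Working it through.** **Inputs from the Sample size paragraph.** Difference 0.05 m/s, SD 0.19 m/s, baseline to 6-month correlation 0.85, two-sided 0.05, 53 completers per group, stated power 80%.

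**The plan's own figure.** The residual SD after baseline is 0.19 × √(1 − 0.85²) = 0.1001. The number per group for 80% power is 2 × [0.1001 × (1.960 + 0.842) / 0.05]² = 62.9, so 63 and not 53. At 53 per group the standard error is 0.1001 × √(2/53) = 0.01944 and the noncentrality is 0.05 / 0.01944 = 2.572. With 103 error df, power is 72.2%. The stated 80% is not reproduced. That is a separate matter, but it makes 72.2% the right starting point here.

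**Adding sex.** Let R² be the share of the baseline-adjusted residual variance that sex explains. The documents give no value, so I take 0%, 2%, 5% and 10%. Because 1 − 0.85² = 0.2775, these are 0%, 0.6%, 1.4% and 2.8% of the total variance. The residual SD becomes 0.1001 × √(1 − R²), with 102 error df. The calculated column below assumes exact balance on sex.

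In practice, blocking and dropout leave a small imbalance. With 50-80% women, block sizes of 2, 4 or 6, and 18 of 124 participants lost at random (all assumed), sex explains 0.14-0.30% of the variance of the arm indicator. The CI width ratio is √[(1 − R²) / (1 − imbalance)] × t(102) / t(103). It does not depend on the SD or correlation of the outcome, so it also applies to the DXA measures at 53 per group.

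The simulated columns use 20,000 trials per cell, with 70% women and blocks of 4 within sex and wave. The paired Monte Carlo error of the power difference is 0.07-0.15 point.

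| R² (assumed) | Calculated power with sex (planned model 72.2%) | Simulated power, planned / with sex | Simulated gain (points) | Change in 95% CI width | Simulated type I error, planned |
|---|---|---|---|---|---|
| 0% | 72.2% | 71.8 / 71.7% | −0.1 | +0.1 to +0.2% | 4.9% |
| 2% | 73.0% | 71.4 / 72.1% | +0.7 | −0.9% | 5.1% |
| 5% | 74.3% | 72.0 / 73.5% | +1.5 | −2.4% | 4.5% |
| 10% | 76.6% | 72.7 / 76.4% | +3.6 | −5.0% | 4.3% |

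**Break-even.** Allowing for the imbalance and the lost degree of freedom, adding sex starts to gain power once R² passes 0.16-0.32%. Below that, the two-term model is very slightly better.

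**Validity.** The planned model's type I error stays near or below 5%. The mean estimated effect was 0.0499-0.0503 for a true 0.05.

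**Limit of the change.** For sex alone to bring power to 80% at 53 per group, R² would have to be 17.4-17.6%.

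**The case against.** The strongest reply is that nothing here is wrong. The primary model is prespecified, matches the sizing model, is unbiased and is at worst slightly conservative. The gain rests on an assumed prognostic share that the documents do not supply and that could be zero. Sex mix and block size are also assumed. All of that stands, and it is why this is an efficiency suggestion and not a defect.

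It can also be said that item 7 already allows for gender, and that the specific statement of the primary test should govern over a general remark on data collection. That is a reasonable reading. But item 7 gives no rule, and a plan followed as written leaves the stratification factor out of the primary test.

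A reader might infer that wave should be added too, because "Randomization of the entire wave (n=24-26) will occur approximately 1 week prior to the start of intervention". The documents do not support that. Wave is not a named stratum, no figure suggests that it predicts outcome, and four extra indicators cost power if it does not. I found no result showing that wave adds power over a model that already contains sex.

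**Conclusion.** The point holds as a low-severity matter of efficiency. Randomisation is stratified by sex and the analysis models do not use it. For gait speed the loss is about 1, 2 and 4 points of power if sex explains 2%, 5% and 10% of the variance left after baseline, and nothing if it explains less than about 0.2-0.3%. For body composition power cannot be computed, because the documents give no DXA SD or correlation; only the CI-width changes carry over.

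Two stronger readings should be resisted. One is that omitting a stratification factor invalidates the test: the estimate is unbiased and type I error is not inflated. The other is that adding sex would repair the gap between about 72% and the stated 80%: that would need sex to explain about 17.5% of the residual variance, well above the range considered, and nothing in the documents suggests a share of that size.

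**What to change.** Prespecify in Data analyses that the primary outcome and each body-composition outcome are analysed as week-24 value = arm + baseline value + sex. Use the same model in the multiple-imputation sensitivity analysis. State that the remark in Study Measure(s), item 7, about using demographics as covariates does not alter the primary test.

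The cost is one or two sentences and 1 degree of freedom, which is about 0.1 point of power if sex is not prognostic. Gender is already recorded, so no new data are needed.
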